field and advances science on the widely used practice of EC use for harm reduction among the two largest ethnic minority groups in the US, Latinx and African Americans. Furthermore, this will be among the first studies to determine how uptake of ECs affects cognitive-perceptual factors involved in sustained tobacco use, such as risk perceptions, utility of smoking, self-efficacy to quit, and tobacco dependence among under-represented minority smokers. This study is directly relevant to the NIH's mission to address cancer risk factors and supports the long-term objective to reduce the disease burden of tobacco use. In the current proposal, Latinx ($n=90$) and African American ($n=90$) cigarette smokers will be randomized in a 2:1 fashion to an EC group ($n=60$ per racial/ethnic group; $N=120$) or an assessment-only control group ($n=30$ per racial/ethnic group; $N=60$). Those randomized to EC will receive a 6-week supply of a fourth generation EC starter kit with their choice of liquid flavor from a standard list. Those randomized to assessment only ($n=60$) will not be provided with an EC. Tobacco consumption in both groups will be assessed at weeks 0 (baseline), 2, and 6. Changes in toxic exposure (NNAL, a primary lung carcinogen and the primary outcome) and carbon monoxide (CO) will be measured from baseline to week 6. Planned covariates include study site, gender, income, tobacco dependence score, and mental health symptoms.

Aim 1. To characterize the toxic exposure of cigarette smokers randomized to the EC group compared to cigarette smokers randomized to assessment-only controls

Hypothesis 1: It is hypothesized that toxicant exposure from baseline to week 6 will be significantly lower in the EC group compared to the assessment-only group.

Hypothesis 2: It is hypothesized that change in cigarette consumption in the EC group from baseline to week 6 will be associated with reduction in toxicant exposure from baseline to week 6.

Aim 2. To assess the effects of uptake of e-cigarettes on perceptions of harm and utility of products

It is hypothesized that from baseline to week 6, the EC as compared to control arm a) will have decreased perceptions of harm to their health from current tobacco use, b) will increase positive utility of EC and increase negative utility of cigarette products, and c) will have decreased expectations of the difficulty of quitting cigarette smoking.

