Prospective participants will be determined eligible or ineligible within 48 hours of initial contact. If eligible, the baseline visit will be scheduled, and a postcard reminder sent out. Screening will occur over the phone, in person, or with an online screening survey developed in REDCap.

Final eligibility is not decided until baseline visit, contingent on blood pressure under 160 (systolic) and 105 (diastolic), carbon monoxide over 5 PPM to validate smoking status, and researcher-assessed stability. Participants who do not meet criteria will not be included in the study and given a smoking cessation referral. San Diego ineligible participants will be referred to the California Smokers' Helpline and Kansas City ineligible participants will be referred to the Kansas Tobacco Quitline. Transportation will be provided to and from study visits when needed in San Diego.

A. Inclusion Criteria

- ≥ 21 years of age
- Smoked cigarettes on ≥ 25 of past 30 days
- Smoked ≥ 5 cigarettes per day on days that smoked
- Smoked cigarettes for ≥ 6 months
- Carbon monoxide > 5 PPM at baseline
- Blood pressure systolic or diastolic < 160/105
- Hispanic/Latinx at San Diego or Black/African American at Kansas City
- Fluent in English or Spanish
- Willing to switch from smoking cigarettes to e-cigarettes for 6 weeks
- Regular access to a telephone
- Transportation to attend Swope Health Central in next six weeks (Kansas City)

B. Exclusion Criteria

- Primary use of other tobacco products or equal use of cigarettes and other tobacco products
- E-cigarette use on ≥ 4 of the past 30 days
- Currently in a smoking cessation program or other clinical trial
- Use of nicotine replacement therapy or medicine which aids smoking cessation in the past 30 days
- Hospitalizations for a psychiatric issue in the past 30 days
- Heart-related event in the past 30 days. Examples include heart attack, stroke, severe angina (i.e. chest pain), ischemic heart disease, and vascular disease
- Planning to move out of San Diego or Kansas City in the next 6 weeks
- Another person in the household enrolled in the study
- Women: pregnant, breastfeeding, or planning to become pregnant in the next six months
- Screener judgment about unstable mental status or health status

VI. Study Design and Timeline

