Height	Health o meter® 500KL	X		

	Professional Digital Scale			
Weight	Health o meter® 500KL Professional Digital Scale	X		X
Spirometry: FVC, FEV1, FEV1/FVC%, PEF, and FEF25- 75%	Futuremed® Discovery-2™ Desktop Spirometer	X	X	X
Saliva (10 San Diego participants)	Saliva collection aid (straw): SB-WS No.61/524,096 Collection tube: Wheaton 1.8 mL yellow cap collection tube	X		X
Nasal Swab (20 Kansas City Participants)	Leukosorb tubes, Q-tips, saline	X		X
Urine	Dynarex Specimen Container 4oz. 118cc reorder No. 4253 Aliquots: Wheaton 20 ml disposable scintillation vials	X	X	X

Table 2. Biological measures, timepoints, and equipment for Project Switch.

CO measurement. Exhaled breath samples will be taken at all visits for carbon monoxide (CO), a by-product of smoke, using a Bedfont Micro+ Smokerlyzer. At baseline, CO measurement will be taken to confirm eligibility. A carbon monoxide level over 5ppm verifies smoking status. A carbon monoxide level 5ppm or lower at baseline makes a person ineligible to participate in the study. Participants will be allowed the opportunity to re-screen two weeks later.

Blood pressure. Systolic and diastolic blood pressure will be measured for screening purposes and throughout the study using a digital blood pressure cuff. If, at the baseline or week 2 visit, a participant's systolic blood pressure is greater than or equal to 160 mm Hg or their diastolic blood pressure is greater than or equal to 105 mm Hg, they will not be eligible to participate or continue participating in the study. Pulse will also be measured but not as an exclusion criteria. Participants who are ineligible at baseline due to uncontrolled blood pressure will be allowed the opportunity to re-screen two weeks later.

Height and weight. A medical scale will be used for a one-time measure of height. Weight will be measured at baseline and week 6 visit, with shoes removed.

Spirometry. Lung function will be measured at all lab visits using a Discovery-2 SpiroVision spirometer. At each session, participants will complete a minimum of three maneuvers (depending on the quality) consisting of a strong exhale and a strong inhale.

Participants will be given a mouthpiece at baseline that will be stored and used at subsequent visits. Participants will be given the option to manually hold their nose closed or to apply a nose clip.

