Spirometer measures include: (1) forced vital capacity, FVC (2) Forced expiratory volume in one second, FEV1 (3) The percentage of the FVC expired in one second, FEV1/FVC% (4) peak expiratory flow, PEF (5) Forced expiratory flow over the middle one half of the FVC, FEF25-75%.

Saliva sampling. Saliva sampling is an exploratory addition to this study and will be taken from ten San Diego participants at baseline and week 6. The decision to take saliva sampling in San Diego resulted in an increase from the original $n=90$ to an $n=94$. Samples will be frozen and transported the testing facility on dry ice.

Nasal swab sampling. Nasal swab sampling is an exploratory addition to this study and will be taken from twenty Kansas City participants at baseline and week 6. The decision to take nasal swab sampling in Kansas City resulted in an increase of two participants for a final $n=92$. Samples will be frozen and transported the testing facility on dry ice.

Urine sampling. Urine will be collected at all lab visits and refrigerated until aliquoting. Participants will be instructed to provide at least half of the specimen cup of urine (about 60mL). Participants will be offered water at the beginning of lab sessions to help facilitate sampling.

Urine will be processed by aliquoting the sample into two smaller samples, each 15 mL. One sample will test for cotinine and need to be pre-treated with sodium bisulfate to obtain a pH between 2 and 3. The second sample will test for NNAL and will receive no additional treatment. Both samples will be frozen and stored at $-20\text{ }^{\circ}\text{C}$ before shipping with dry ice for testing.

A urine log will provide the following information for each urine sample: (1) participant ID (2) study time point (3) date: mm/dd/yyyy (4) testing for: NNAL or cotinine. Each lab visit will produce two samples stored for further testing.

Although urine will be taken at all three lab visits, only baseline and week 6 urine will be sent for testing. In the case of missing week 6 samples, week 2 samples will be sent instead as a method of imputation.

Sample shipment. Specimens will be transported in a leak-proof Styrofoam container in leak-proof secondary packaging, with absorbent material placed at the bottom and sides of the container for absorption. 10-15lbs dry ice will be used to maintain storage temperature during transport.

IX. Laboratory Analysis

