Urine: cotinine ng/mL, creatinine mg/mL, nitrosamine 4-(methylnitrosamino)-1-(3-pyridyl)-1-butanol (NNAL) pg/mL, and 3-hydroxycotinine ng/mL

Saliva: Cytokine Panel and C-Reactive Protein

Nasal Swab: MMP9 ELISA in pg/mL and TGF-B1 ELISA in pg/mL

X. Study Visits Overview

Baseline	Week 1	Week 2	Week 4	Week 6
Participant consent	Follow-up check-in	Urine test	Follow-up check-in	Saliva sample (San Diego)
Saliva sample (San Diego)	Yesterday tobacco use	Blood pressure test (must be less than 160/105)	Yesterday tobacco use	Urine test
Complete contact sheet		Carbon monoxide test		Blood pressure test
Blood pressure test (must be less than 160/105)		Eligibility check		Carbon monoxide test
Carbon monoxide test (must be greater than 5 ppm)		Follow-up check in sheet (EC group)		Nasal swab (Kansas City)
Nasal swab (Kansas City)		Timeline follow back		Weight
Final eligibility check and Study ID assignment		Spirometry test		Follow-up check in sheet (EC group)
Randomization		Week 2 survey		Timeline follow back
Charge JUUL (EC group)		Collect used JUUL pods (EC group)		Spirometry test
Timeline follow back		Provide more JUUL pods (EC group)		Week 6 survey
Pod count form (EC group)		Schedule visits/phone calls		Collect used JUUL pods (EC group)
Height and weight		Compensation		Tobacco cessation referral
Baseline survey part 1				Exit survey
Spirometry test				Compensation
Baseline survey part 2				
Cigarette questions and breathing conditions				
E-cigarette switching fact sheet (EC group)				
E-cigarette use instructions (EC group)				
E-cigarette trial and subjective effects questionnaire (EC group)				

Baseline action planning (EC group)				
Schedule visits/phone calls				
Reimbursement schedule				
Urine test				
Compensation				

Table 3. Surveys and tests by study timepoint.

At each lab visit, participants will receive compensation and sign a receipt. At the end of the study, participants will be given a referral to the California Smokers' Helpline ([name]) or Kansas Tobacco Quitline ([name]).

XI. Study Questionnaires

Surveys will contain items on demographics, smoking measures, tobacco measures, physiological measures, and psychosocial assessments. Given the possibility of low literacy among participants, surveys will be verbally administered along with visual cue cards.

XII. Data Management

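### The week 2 blood-pressure limit ends study participation, not only product use, for randomised participants in both arms, and no text keeps them in follow-up to week 6 (minor)

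*Protocol*

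**What the plan says.** Section V makes blood pressure part of entry: "Final eligibility is not decided until baseline visit, contingent on blood pressure under 160 (systolic) and 105 (diastolic". Section VIII (Blood pressure) applies the same limit again at week 2, and the consequence is that "they will not be eligible to participate or continue participating in the study". Re-screening after two weeks is offered only to those who fail at baseline.

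Table 3 in section X puts randomisation in the baseline column. Its week 2 column lists "Blood pressure test (must be less than 160/105" and, further down, an eligibility check. Neither is marked for the e-cigarette (EC) group, although other items in that column are, such as the supply of further pods. Controls fall under the rule too, and section I says that they "will not be provided with an EC".

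The outcomes are set at week 6. Section I says that NNAL and "carbon monoxide (CO) will be measured from baseline to week 6", and Aim 2 opens with "It is hypothesized that from baseline to week 6, the EC as compared to control arm". On consumption it says: "Tobacco consumption in both groups will be assessed at weeks 0 (baseline), 2, and 6". Section VIII (Urine sampling) adds: "In the case of missing week 6 samples, week 2 samples will be sent instead as a method of imputation".

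**The concern.** A limit that is an ordinary entry criterion before randomisation becomes, at week 2, a reason to remove randomised people on a measurement taken after allocation. The wording does not separate stopping the product from leaving the study. A safety reason can explain why no more pods are given to someone with high blood pressure. It does not explain why urine, CO and survey collection should end, least of all in a control.

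At stake is week 6 information on a few randomised participants. A statistical analysis plan can say how to handle missing values, but it cannot recover a visit that the conduct rule prevented.

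**Working it through.** **1. Does the rule reach randomised people in both arms?** Yes. Randomisation is a baseline item in Table 3, the rule names week 2, and neither section VIII nor Table 3 limits it to the EC group.

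**2. What is lost and what remains for someone removed at week 2?** That the week 6 visit does not take place is an inference, but it is the plain meaning of not continuing in the study.

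| Item | Week 6 value | What remains |
|---|---|---|
| NNAL (primary) | not collected | week 2 urine, assayed in its place; the visit window of one week either side (section VII) puts it at about week 1 to week 3 |
| CO | not collected | week 2 reading, listed above the eligibility check |
| Survey (Aim 2) | not collected | week 2 survey, unless Table 3 is the running order of the visit, because it is listed below the check |
| Timeline follow-back | not collected | same condition as the survey |
| Tobacco use by phone | week 4 call lost | week 1 call, made in both arms (section VI) |

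**3. How many people?** The protocol gives no rate and no blood-pressure distribution, so every input here is an assumption:
- systolic mean 125 to 135, SD 15 to 17, visit-to-visit SD 8 to 12;
- diastolic mean 80 to 84, SD 10, visit-to-visit SD 5 to 7;
- systolic-diastolic correlation 0.7 between persons and 0.6 within a visit;
- no true change between visits, and one reading per visit.

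With 1,000,000 simulated people per scenario, all required to be below both limits at entry, the share at or above either limit at week 2 is:

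| Assumed SD is | Eligible at first reading | All baseline failures re-screened once |
|---|---|---|
| total SD of one reading | 1.01% to 6.04% | 1.21% to 6.99% |
| between-person SD | 1.67% to 8.03% | 2.10% to 9.86% |

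The extremes as counts:
- whole trial: 180 × 0.0101 = 1.8 to 180 × 0.0986 = 17.7;
- EC arm: 120 × 0.0101 = 1.2 to 120 × 0.0986 = 11.8;
- controls: 60 × 0.0101 = 0.6 to 60 × 0.0986 = 5.9.

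The attrition allowance is 180 × 0.20 = 36. Removals would use between 1.8/36 = 5% and 17.7/36 = 49% of it. Section VIII raises enrolment to 94 + 92 = 186, which changes nothing of substance (186 × 0.0986 = 18.3).

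**4. Is there an effect on the NNAL comparison?** The planned effect is 0.37 SD with no change expected in control (Sample Size). Let p be the share of the EC arm removed, f the share of the week 6 effect already present at week 2, and g the share still present at week 6 in someone whose pods were withheld from week 2. Keeping these people to week 6, rather than using their week 2 urine, changes the estimated effect by

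p × (g − f) × 0.37.

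With p = 0.05 and f = 0.5:
- g = 0.75 gives 0.05 × 0.25 × 0.37 = +0.005 SD;
- g = 0.25 gives 0.05 × (−0.25) × 0.37 = −0.005 SD.

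The sign turns on g and f, and the protocol gives neither.

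**5. The plan's power figure.** The stated power above 0.82 comes from a simulation whose correlation over time is not given, so it can be neither confirmed nor refuted. With baseline adjustment and an assumed two-sided 0.05, 0.82 needs a baseline-to-follow-up correlation of about 0.58 without loss, or 0.69 with 20% loss. The point does not depend on this figure.

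**The case against.** The strongest defence is that this is a safety rule affecting few people, and that the plan already allows for attrition. The small number stands. The safety purpose also stands, but it supports stopping the product, not ending measurement, and it has no product to act on in controls.

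Three stronger readings are tempting, and the document does not support them:
- **NNAL is biased in a known direction.** A reader might infer that week 2 urine dilutes the effect toward the null, or that the rule creates a false benefit. The dilution argument assumes that a removed EC participant, if kept, would show the full week 6 effect. Pods would be withheld from that person, so the assumption is not available.
- **Removal is related to arm.** Nothing in the protocol shows that the assigned arm affects blood pressure, so unequal removal is possible but not established.
- **Removed people have no data after baseline.** The week 1 call gives some consumption data, and week 2 urine and CO are listed ahead of the eligibility check. The week 2 survey and timeline follow-back are lost only if Table 3 is the running order. Its caption says only that it shows surveys and tests by time point.

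The lack of a stated substitute for week 6 CO and survey is also not a defect in itself. Handling of missing values commonly sits in the statistical analysis plan, which is not at hand. Here the missing values are a consequence of the removal rule.

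**Conclusion.** The point holds as a minor one. As written, the week 2 limit ends participation for randomised people in either arm and nothing keeps them in follow-up. On the plain reading, week 6 CO, survey and timeline follow-back are lost for them, and their primary outcome moves from week 6 to week 2.

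Under the assumed distributions this concerns roughly 1% to 10% of participants, within the attrition allowance. The conclusion rests on the wording of section VIII and Table 3. The number rests wholly on the assumptions, and no size or direction is claimed for NNAL.

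**What to change.** Apply 160/105 as an eligibility criterion at baseline only. At week 2 keep the check as a safety rule that stops or withholds e-cigarette supply in the EC group, with referral in either arm as clinically needed. In section VIII, replace the week 2 part of "they will not be eligible to participate or continue participating in the study" with a statement that all randomised participants stay in follow-up for the week 6 urine, CO, timeline follow-back and survey, and are analysed in their randomised arm. In Table 3, rename the week 2 eligibility check as a safety check.

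The cost is a wording amendment and the already planned week 6 visit for about 2 to 18 people under the assumptions above. The check before more pods are handed out is unchanged.

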Study E-cigarettes. Participants in the e-cigarette group will be provided JUUL, a nicotine-salt based e-cigarette (see Figure 2). Participants will have the flavor selection of Virginia tobacco, cool mint, menthol, or mango pods containing .07 mL nicotine (5% nicotine). Pod use will be tracked using the Pod Count Form, requiring participants to bring to lab visits all used, unused, and partially used pods. Pods will be distributed based on cigarette use, and determined using the Pod Count Calculation Form. Education about switching will be verbally provided to the e-cigarette group. Participants will engage in motivational enhancement-based action planning and will receive JUUL usage instructions. Participants in the e-cigarette group will be provided a compatible wall adapter to ensure proper charging, a device carrying case, Q-tips to clean the device as needed, and a gallon Ziplock bag to store used pods.

Figure 2. JUUL electronic cigarette. Reprinted from *JUUL Labs, Inc*, Retrieved December 9, 2018, from www.juul.com. Copyright 2018.

VII. Participant Retention

Participant retention will be maintained by using a variety of contact methods including call, text, email, physical letter in the mail, and reaching out to emergency contacts. No more than six contact attempts, of various forms, will be made. Contacting emergency contacts and sending a letter will be the last efforts made to contact an unreachable participant. Additionally, participants will be sent postcards reminding them of the day and time of their next lab visit, and appointment reminder cards will be given out at the baseline and week 2 visit reminding about upcoming phone calls.

Lab visits will have pre-determined time windows. The week 2 visit can be scheduled up to one week before or after the originally scheduled date of two weeks after the baseline visit. The week 6 visit can be scheduled up to four weeks before or after the originally scheduled date of six weeks after the baseline visit. Ripple protocol details the scheduling protocol.

VIII. Laboratory Procedures and Sampling

Data from biological measurements and samples will be recorded on paper and/or in REDCap.

The table below shows the equipment used for the biological measures, and timepoints taken.

Measure	Equipment	Baseline	Week 2	Week 6
Carbon Monoxide	coVita Bedfont Micro+ Smokerlyzer®	X	X	X
Systolic Blood Pressure, Diastolic Blood Pressure, and Pulse	Omron® BP742N 5 Series Upper Arm Blood Pressure Monitor	X	X	X

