Missing data will be minimized through extensive training of research staff in addition to follow-up with participants. Data will be entered into REDcap electronically and paper forms (biological measures and pod count forms) will be stored in participant files. Paper forms with identifiable information such as consent and contact information will be stored in a separate, locked location. TLFB data will be entered into excel, with paper calendars and data entry forms stored in participant files. REDcap entry will happen after the lab session and will be audited and checked by project managers daily. REDCap is a secure, HIPAA-compliant, web-based application designed to support data capture for research studies. All protocol-specified data will be linked by unique subject ID, assigned at randomization. Paper files will be stored on site in a locked filing cabinet and any forms with identifying information (consent form and contact sheet) will be kept in a separate location. Data is only accessible to personnel involved with this research. Access is limited by the research facility being locked at all times.

XIII. Recording and Reporting of Adverse Effects

Development of any adverse effects will be monitored closely by a project manager such that fields capturing adverse events will be reviewed daily. At each study visit, participants will be asked about the development of any other, new, or worsening symptoms. At each visit and each phone call after the initial visit, participants in the e-cigarette condition will be asked if they were experiencing any barriers to switching to e-cigarettes or any concerns about switching. This open-ended format is intended to capture any unexpected adverse events. Unexpected serious adverse events will be reported to the CSUSM IRB and assessed by the PI to determine if related to e-cigarette use, and if so, reported to the NIH and FDA. Participants will be encouraged to contact staff if they have any questions, problems using their e-cigarette, or if any adverse events develop.

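### Read as a working order, Table 3 puts randomisation and two e-cigarette-only steps before the verbally administered baseline surveys, so Aim 2 baselines may be taken with the arm known

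*Protocol*

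**What the plan says.** Protocol Section X, Table 3, lists the baseline visit as a column of entries. After consent and the gating tests comes "Final eligibility check and Study ID assignment", then Randomization, then "Charge JUUL (EC group". Timeline follow back, the pod count form, and height and weight follow. Only then come survey part 1, spirometry and survey part 2.

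Section XI says of the mode: "Given the possibility of low literacy among participants, surveys will be verbally administered along with visual cue cards". Of the content it says: "Surveys will contain items on demographics, smoking measures, tobacco measures, physiological measures, and psychosocial assessments".

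Aim 2 (Section I) is a between-arm contrast of change "from baseline to week 6, the EC as compared to control arm", in perceived harm, product utility and expected difficulty of quitting. The Project Summary adds: "Planned covariates include study site, gender, income, tobacco dependence score, and mental health symptoms".

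The available text does not say that allocation is withheld until the surveys are done, or that the interviewer is unaware of the arm.

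**The concern.** A baseline measure should be fixed before anyone who can influence it knows the allocation. Otherwise randomisation no longer guarantees that the arms are comparable on it. The Aim 2 outcomes are subjective and are collected by interview, so they are open to the expectations of both interviewer and respondent.

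A reaction is plausible in either arm. Every participant must be willing to switch for six weeks (Section V.A), and controls then learn that they will receive no device. If that knowledge colours the first answers, part of an arm effect is absorbed into the baseline and then subtracted out or adjusted for. Dependence score and mental health symptoms, if they come from the same surveys, would become post-allocation covariates.

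**Working it through.** **Step 1. Row positions.** Counting the Baseline column of Table 3:

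| Row | Entry | Arm |
|---|---|---|
| 4, 5 | Blood pressure, carbon monoxide | both |
| 7 | Final eligibility check, study ID | both |
| 8 | Randomization | both |
| 9 | Device charging | e-cigarette only |
| 10 | Timeline follow back | both |
| 11 | Pod count form | e-cigarette only |
| 13 | Survey part 1 | both |
| 14 | Spirometry | both |
| 15 | Survey part 2 | both |
| 16 | Cigarette and breathing questions | both |
| 17–20 | Fact sheet, use instructions, product trial, action planning | e-cigarette only |
| 23 | Urine | both |
| 24 | Compensation | both |

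All the self-reports (rows 10, 13, 15 and 16) stand after row 8. Both surveys stand after two e-cigarette-only steps.

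**Step 2. Is the column a working order?** The caption does not say so. The internal evidence favours it:
- Consent is first and compensation last.
- The tests that decide eligibility precede the eligibility check.
- Every e-cigarette-only step follows Randomization.
- The pod form directly follows timeline follow back. This fits Section VI: "Pods will be distributed based on cigarette use, and determined using the Pod Count Calculation Form".
- The survey is split in two with spirometry between the parts, which makes little sense in a plain inventory.
- Urine is row 23 at baseline, row 1 at week 2 and row 2 at week 6.

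**Step 3. Do the surveys hold the Aim 2 items?** Section XI names only broad classes of content. Psychosocial assessments are among them, and no other baseline instrument in the available text is described that would carry the items. Their place in the surveys is therefore an inference, as it is for the dependence and mental health covariates.

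**Step 4. What the arm could affect.** Rows 17–20 come after both surveys. On this reading, neither switching education nor product use precedes the Aim 2 baseline. What precedes it is knowledge of the arm, device charging and the pod form.

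**Step 5. Form of the bias.** The protocol states no figure on this point, so there is none to reproduce. Let theta be the true arm effect at week 6 in SD units, delta a shift confined to the e-cigarette arm's baseline score, and rho the correlation between baseline and week 6, with equal SDs at both visits.
- Change score: expected contrast = theta − delta, so the bias has size delta.
- Baseline-adjusted: expected contrast = theta − rho × delta, so the bias has size rho × delta.

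A shift in the hypothesised direction shrinks the contrast and the opposite shift inflates it. For a shift in the control arm the signs reverse.

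The documents give neither delta nor rho. For scale only, assume delta from 0 to 0.2 SD and rho from 0.4 to 0.6:
- Change score: bias 0 to 0.20 SD.
- Adjusted: 0 to 0.4 × 0.2 = 0.08 SD, up to 0 to 0.6 × 0.2 = 0.12 SD.

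The Sample Size paragraph claims power above 0.80 for Aim 2 effects of d > 0.30. Against that 0.30, a shift of 0.10 SD is 0.10/0.30 = 33% for a change score and 0.04/0.30 = 13% to 0.06/0.30 = 20% for an adjusted analysis. At delta = 0 nothing changes.

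**The case against.** The strongest reply is that Table 3 is an overview of content by timepoint. It is not a complete step list: week 2 has a row for providing more pods, while the Baseline column has no dispensing row at all. Part of the protocol text before the Sample Size paragraph was not available, Figure 1 is not shown, and Section VII refers to a separate scheduling protocol. Any of these could govern when allocation is disclosed. Charging may also be a staff task out of the participant's sight. This stands as a limit on certainty. It does not remove the point, because staff who administer the surveys would still know the arm, and the visible order is the only one the protocol gives.

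A reader might infer more in four ways, and the documents do not support any of them.
- **That counselling or e-cigarette use contaminates the Aim 2 baseline.** Rows 17–20 follow both surveys.
- **That the primary outcome is affected because baseline urine (row 23) is listed after the product trial (row 19).** Section VIII does not fix when in a visit urine is given, and it offers water at the start to help sampling. In the aims, cotinine verification belongs to Aim 3, within the e-cigarette group. No effect on NNAL or on a between-arm hypothesis is shown.
- **That Section XII already contradicts Table 3 on the study ID.** It reads "All protocol-specified data will be linked by unique subject ID, assigned at randomization", and rows 7 and 8 are adjacent, so the two fit as they stand. A mismatch arises only once randomisation is moved.
- **That Aim 2 loses a calculable amount of power or of error control.** The protocol gives no standard error or correlation for Aim 2, and a standard error solved back from its power statement need not agree with an assumed rho. No such figures should be quoted.

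**Conclusion.** The point holds in conditional form. If the Baseline column is followed as listed, the baseline self-reports are taken after allocation, with the arm known to staff and possibly to the participant, and the Aim 2 baseline could already contain an arm effect. This rests on two inferences: that the column is a working order, which its internal sequence supports, and that the surveys carry the Aim 2 items and the two covariates. The exposure is knowledge of the arm only. The size and direction of any bias are unknown. Only its form can be stated: delta for a change score, rho × delta after baseline adjustment. The documents do not show that any bias has occurred or that NNAL is touched. Severity is low to moderate, and the case for acting is that the remedy is cheap.

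**What to change.** Re-order the Baseline column of Table 3. After the final eligibility check, complete timeline follow back, both surveys and the cigarette and breathing questions before randomisation is carried out or disclosed. Where practicable, do the same for the remaining measurements and urine. Place all e-cigarette-only steps after it. State under the table that the rows are a running order.

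As a consequence, Section XII should say that the study ID is assigned at the final eligibility check, so that data collected before randomisation can be linked. If visits already run this way, correct the table to show it.

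The cost is a re-ordered checklist and two edited sentences, with no added measurement. One small downside is that device charging can no longer overlap with the surveys unless it is arranged without revealing the arm. The protocol gives no charging time, so the delay cannot be sized.
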